### 3.2.2 Safety Assessments

Safety assessments will be evaluated, based on reports of AEs and results of vital signs (supine and standing blood pressure, pulse, and temperature), weight, clinical laboratory evaluations (blood chemistries, hematology and urinalysis including microscopy), a 12-lead ECG, and physical and neurological examinations. Post-void residual (PVR) bladder ultrasounds to assess urinary retention and the American Urological Association (AUA) Symptom Index to assess urinary voiding function will also be performed during the first year of the open-label extension study.

### 3.2.3 Quality of Life Assessments

The QOLIE-31-P (Version 2.0) will be utilized to assess quality of life. The QOLIE-31-P assessment must be completed by the patients. Patients who are cognitively impaired and cannot complete the QOLIE-31-P assessment may still participate in the study, by obtaining a waiver for QOLIE-31-P completion from the study medical monitor.

## 4 STATISTICAL METHODS

### 4.1 Study Patients

#### 4.1.1 Disposition of Patients

Patients are free to discontinue their participation in the study at any time and without prejudice to further treatment at their local site. The Investigator must withdraw any patient from the study if that patient requests to be withdrawn. Patients withdrawn from the study will not be replaced, regardless of the reason for withdrawal. The patient's participation in this study may be discontinued due to the following reasons:

- Patient experiences an intolerable AE.
- Investigator decides patient has an “unsatisfactory response – efficacy.”
- Patient becomes pregnant.
- Patient is unwilling or unable to continue the study.
- Patient is non-compliant with study procedures.
- Patient needs medication not allowed in the protocol.
- Any clinically significant change in patient's medical condition.
- Persistent ALT or aspartate aminotransferase (AST) above 3 times the ULN; will be confirmed by repeating laboratory assessment within 1 week.
- ALT or AST levels are above 5 times the ULN at any time during the study.
- Confirmed QTc prolongation defined as QTc (Bazett's) >500 msec or an increase in QTc (Bazett's) of >60 msec from baseline.

- Investigator decides that withdrawal from the study is in the best interest of the patient.
- Request of the Sponsor.
- Hematological reasons or infections – for all such patients, the investigator shall report these in an expedited manner, whether or not they are considered serious or unexpected.

A summary of the number and percentage of discontinuations by primary reason will be provided together with descriptive statistics for the time until treatment discontinuation (days).

A by-patient listing of patient withdrawal/study completion details will also be provided.

#### 4.1.2 Analysis Populations

The Safety Population is defined as all patients who successfully completed the transition phase of Study VRX-RET-E22-302 and were enrolled into the long-term study VRX-RET-E22-304. The Transition phase is the phase of Study VRX-RET-E22-302 during which patients were adjusted to a 300 mg TID dose.

There will be no other population for this study.

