#### 9.7.1. Dosage Schedule and Mode of Administration

Patients who completed the Transition phase of Study VRX-RET-E22-302 will start with 300 mg three times a day (300 mg TID). Patients who were not able to tolerate the final dose adjustment (750 mg/day) during the last week of the Transition phase of Study VRX-RET-E22-302 will start with 200 mg three times a day (200 mg TID).

If, in the opinion of the Investigator, the patient was not receiving the maximum effective dose, the dose could be increased in weekly intervals of 150 mg/day, up to a maximum of 1200 mg daily (i.e. 400 mg TID). If adverse events considered to be secondary to retigabine occur, the total daily dose could be reduced by 150 mg/day every week, at Investigator discretion, as long as the dose is within 600-1200 mg/day.

At the investigator's discretion, patients may also start with another dose regimen that can be either BID or TID, and is not required to be equally distributed throughout the day (e.g., if a patient experiences somnolence and the investigator decides to dose the patient higher in the evening) as long as the total daily dose is within 600 -1200 mg/day.

After the patient has entered open-label treatment, the Investigator may add new AEDs, as long as these are approved AEDs. In addition, the existing background AED therapy can be adjusted to achieve the best efficacy/safety ratio, as needed, per Investigator discretion. If necessary, in the Investigator's judgment, all background AEDs can be discontinued to achieve monotherapy with retigabine.

Patients who permanently discontinue open-label treatment will have their dose tapered by one-third every week.

Patients will be instructed on the administration procedures for study drug. Study medication will be administered orally with or without food. The 3 daily doses are to be administered with approximately an 8-hour interval between them (for example 7am, 3pm, 11pm). Patients will continue to take their established background AEDs from their own prescriptions.

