## **11.4. Additional Statistical Considerations**

### **11.4.1. Analysis Population**

The safety population will include all patients who successfully complete the Transition phase of Study VRX-RET-E22-302 and were included in this long-term study. The Transition phase is the phase of Study VRX-RET-E22-302 during which patients were adjusted to a 300 mg TID dose. No other population for analysis is defined for this long-term extension.

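### The only analysis set is defined by completing the parent study's Transition phase and enrolling, not by taking an open-label dose

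*SAP*

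**What the plan says.** SAP 4.1.2 sets two conditions for the Safety Population: "The Safety Population is defined as all patients who successfully completed the transition phase of Study VRX-RET-E22-302 and were enrolled into the long-term study". It then identifies the phase: "The Transition phase is the phase of Study VRX-RET-E22-302 during which patients were adjusted to a 300 mg TID dose". It closes with "There will be no other population for this study".

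Protocol 11.4.1 agrees: "The safety population will include all patients who successfully complete the Transition phase of Study VRX-RET-E22-302 and were included in this long-term study", followed by "No other population for analysis is defined for this long-term extension". The protocol synopsis repeats the definition. None of these places mentions taking open-label drug.

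Protocol 9.7.1 describes two groups entering treatment in 304. Those who completed Transition start at 300 mg TID. The other group is "Patients who were not able to tolerate the final dose adjustment (750 mg/day) during the last week of the Transition phase", and they start at 200 mg TID. Inclusion criterion 1 (protocol 9.5) also requires successful completion of Maintenance and Transition. No document supplied says what makes completion successful.

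**The concern.** Safety and tolerability of long-term treatment is the primary objective, and this is the only population. The table shells in the SAP are headed with it. A safety set is normally built on exposure. This one is built on how the patient finished a phase of the parent study, so it can differ from the set of patients treated in 304 in both directions:

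- **Treated but outside the set.** Anyone who received open-label drug without having successfully completed Transition is outside by definition. The 200 mg TID starters may be outside too, depending on what successful completion means.
- **Inside the set but untreated in 304.** Enrolment and supply are enough for membership.

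If those left out tolerate the drug less well, or those untreated inflate the denominator, the reported AE percentages no longer describe the exposed patients.

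**Working it through.** The protocol (11.3) says a sample size determination does not apply, and the plan states no figure that depends on this definition, so there is nothing to reproduce. The check is a comparison of passages, followed by illustrative arithmetic.

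**Can a dosed patient be left out?**

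1. The set requires successful Transition completion, which is also inclusion criterion 1. A patient enrolled in breach of that criterion and then dosed fails the first condition. Protocol 9.10 foresees enrolment in breach of inclusion or exclusion criteria. This route does not depend on interpretation.
2. Protocol 9.7.1 sets patients who completed Transition apart from those who did not tolerate its final adjustment, yet treats both. Read literally beside SAP 4.1.2, the second group might not be completers. Read beside inclusion criterion 1, they must be completers, because otherwise 9.7.1 gives a starting dose to patients whom 9.5 would bar. This route is therefore conditional.
3. The dose statements do not settle it. 300 mg x 3 = 900 mg/day is what SAP 4.1.2 and protocol 7.1 say Transition reaches. Protocol 9.7.1 gives the final adjustment as 750 mg/day, and 900 - 750 = 150 mg/day.

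**Can an undosed patient be counted?**

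1. Consent, final eligibility and dispensing all take place at Visit 11 of 302 (protocol 10.1 and 10.5), before any open-label tablet is taken.
2. SAP Listing 1 has a column on whether drug was dispensed or used in discontinued patients. The SAP thus plans to show related information but does not use it in the definition.
3. SAP 4.5.2 counts TEAEs from the first dose in the extension. SAP 4.5.1 counts exposure from the first dose date. It labels that date Day 0, a label that SAP 4.3 gives to the start of treatment in 302. A patient with no open-label dose has no TEAE anchor and no open-label exposure. Such a patient is undosed in 304 only, having been in Transition in 302.

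**Illustrative size.** N = 510 is the maximum in SAP 4.7. All shares and event rates below are assumptions, because the documents give none.

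*Undosed patients in the denominator:* reported rate = true rate x dosed / N.

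- 5 undosed (1%): 30% x 505/510 = 29.7%; 50% x 505/510 = 49.5%.
- 26 undosed (5%): 30% x 484/510 = 28.5%; 50% x 484/510 = 47.5%.

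*Less tolerant patients left out:* rate in all dosed = [(N - x) x 15% + x x r] / N, where x patients are excluded and r is their event rate. The reported rate is 15.0%.

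- x = 10 (2%), r = 30%: (500 x 0.15 + 10 x 0.30)/510 = 78.0/510 = 15.3%.
- x = 26 (5%), r = 30%: (484 x 0.15 + 26 x 0.30)/510 = 80.4/510 = 15.8%.
- x = 51 (10%), r = 45%: (459 x 0.15 + 51 x 0.45)/510 = 91.8/510 = 18.0%.

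*A table that can move the other way:* SAP Table 1 counts discontinuations. If 15% of dosed patients discontinue and 5 undosed patients also count as discontinued, the table shows (505 x 0.15 + 5)/510 = 80.75/510 = 15.8%, which is above the 15.0% among dosed patients.

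**The case against.** The strongest defence is that the population wording mirrors inclusion criterion 1, so the set is simply everyone eligible who enrolled. Protocol 7.1 describes Transition as a four-week phase, and entry to 304 happens at its last visit, so enrolment according to protocol already implies reaching the end of it. Because 9.7.1 gives the 200 mg TID group a starting dose, the reading that keeps 9.5, 9.7.1 and SAP 4.1.2 consistent is that these patients completed Transition and are in the set. The SAP sentence about 300 mg TID identifies the phase and need not set a success threshold. The protocol of 302, which would define its steps and its completion, is not among the documents.

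Much of this stands. A reader might infer that the plan drops the 200 mg TID starters; the documents allow that reading but do not require it. A reader might also infer from 750 against 900 mg/day that patients are lost. It shows only a tension in wording: 750 mg/day could be the last Transition step, with the 300 mg TID start following in 304.

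Two mitigations also stand. By-patient listings of all AEs, deaths, SAEs and AEs leading to withdrawal are planned (SAP 4.5.2 and 4.5.3), and the listing titles carry no population label. Categorical percentages use patients providing data at the time point (SAP 4.3), which limits dilution in by-visit tables. Nothing suggests that undosed patients would be more than rare.

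The defence does not answer two points. A patient dosed in breach of criterion 1 is outside the set on any reading, and an enrolled patient who takes no open-label dose is inside it. Listings do not correct summary percentages.

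**Conclusion.** The concern holds in limited form. The only analysis set is not defined by exposure, and one of its two conditions is undefined. Omission of patients dosed in breach of the completion criterion, and inclusion of enrolled-but-undosed patients, follow directly from the text. Omission of the 200 mg TID starters is possible but depends on interpretation.

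Omitting less tolerant patients and adding undosed ones would both be expected to lower AE incidence. Under the assumed ranges the shift is 0.3 to 1.5 percentage points on a 30% TEAE rate from undosed patients, and 0.3 to 3.0 points on an event rate from exclusions. The upper figure needs every one of 51 non-tolerators to be excluded and to have three times the event rate of the others. The true effect is probably small.

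Two stronger readings should not be drawn. One is that the bias always favours the drug: undosed patients can raise the discontinuation rate in Table 1, and a higher AE rate in patients starting on a lower dose is assumed, not shown. The other is that about 13% of patients would be affected: that figure in protocol 7.4 is discontinuation for adverse events in a different titration study going up to 1200 mg/day, not the share failing the last Transition step of 302.

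The change is still worth making, because safety is the primary objective and no second population exists as a check.

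**What to change.** - In SAP 4.1.2, protocol 11.4.1 and the protocol synopsis, define the Safety Population as all patients enrolled in 304 who took at least one dose of open-label retigabine, regardless of Transition outcome or starting dose.
- Add a line to the disposition table for patients enrolled but never dosed in 304.
- The sponsor should reconcile the passages on Transition completion and dose: protocol 7.1, 9.5, 9.7.1 and 11.4.1, and SAP 4.1.2. No dose is proposed here.

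The cost is one sentence in each place and one row in a table shell. No new data are needed, because protocol 9.8 already has the CRF capture first and last dose dates.

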## 4.2 Demographic and Other Baseline Characteristics

Demographic and baseline characteristics were not collected as part of the VRX-RET-E22-304 case report form (CRF). For the following summaries of demographic and other baseline characteristics, unless otherwise noted, the last recorded value prior to commencement of study treatment in the VRX-RET-E22-302 study will be used as baseline.

A summary of the following demographic variables will be presented at baseline:

- age
- sex
- race
- weight
- height
- body mass index (BMI)
- duration of partial and generalized seizures, separately
- type of onset of partial and generalized seizures, separately

- Baseline seizure type cohorts
- number of background AEDs
- number of patients using Vagal Nerve Stimulators
- CGI severity baseline scores

A patient's age in years will be calculated as the number of completed years between the date of the informed consent for the VRX-RET-E22-302 study and date of birth (i.e. date of informed consent minus date of birth divided by 365.25). Age, weight and BMI will be summarized using continuous descriptive statistics. The number and percentage of patients in each sex category (male and female), and each race category (Caucasian, African-American, Hispanic, Asian and Other), will be reported using categorical descriptive statistics.

Duration of partial and generalized epilepsy is defined as the difference between Year of Onset recorded in Epilepsy History and year of Visit 1 (screening) for the VRX-RET-E22-302 study. The duration of partial epilepsy will be summarized using continuous descriptive statistics.

By-patient listings of all demographic data and baseline characteristics will also be provided.

### 4.3 General Considerations

Study day is defined as the number of days relative to Day 0 (i.e., the start of study treatment in the double-blind study VRX-RET-E22-302), computed as (the date – Day 0 date+1).

Continuous data that are assumed to be normally distributed will be summarized in terms of the mean, standard deviation (SD), median, minimum, maximum and number of observations. Continuous data that are expected to be skewed will be presented in terms of the maximum, upper quartile, median, lower quartile, minimum and number of observations. The minimum and maximum will be reported to the same number of decimal places as the raw data recorded in the database. The mean, SD, median, lower quartile and upper quartile will be reported to one more decimal place than the raw data recorded in the database. In general, the maximum number of decimal places reported shall be four for any summary statistic.

Categorical data will be summarized in terms of the number of patients providing data at the relevant time point (n), frequency counts and percentages. Percentages will be presented to one decimal place. Percentages will not be presented for zero counts. Percentages will be calculated using n as the denominator.

#### 4.4 Efficacy Evaluation

“Monthly total partial seizure” as well as “monthly total seizure” rates will be calculated for the entire open-label part of Study VRX-RET-E22-304 and statistically described. “Monthly total partial seizure” rate is defined as the sum of total partial seizures throughout the open-label portion (of Study VRX-RET-E22-304), divided by open-label duration in days, standardized by 28 days (1 month). “Monthly total seizure” rate is defined as the sum of partial and generalized (or unclassified) seizures throughout the open-label duration in days, standardized by 28 days (1 month).

Monthly total partial seizure rates observed during the open-label extension period will be compared to the monthly total seizure rates observed during the Baseline phase of the double-blind study VRX-RET-E22-302. The baseline monthly total seizure rates will only be derived for patients who enter this open-label extension and have a monthly total partial seizure rate during the open-label extension period. The percent change in monthly total partial seizure rates from the Baseline phase will be classified into <0, [0, 25), [25, 50), [50, 75), [75, 100] with a description of the frequencies. The responder rate during the open-label study (defined as a reduction in seizure frequency  $\geq 50\%$ ) will also be summarized using descriptive statistics.

The monthly total partial seizure rates compared to the baseline monthly total partial seizure rate will be presented cumulatively for each timepoint (months 1, 3, 6, 9, 12, 16, 20, 24, 28, 32 and 36) during the open label extension period and separately for eleven cohorts of patients treated with retigabine for at least 1, 3, 6, 9, 12, 16, 20, 24, 28, 32 and 36 months. In each cohort, patients will be followed for entire indicated duration of treatment. For example, patients in the 36-month cohort will also be part of the shorter-duration cohorts.

A similar analysis will be repeated for the responder rate during the open-label study.

A plot of the median percent reduction from baseline in seizure frequency over time by duration of treatment will also be produced.

The number of seizure free days, in percent to the individual duration of the open-label treatment, will be calculated and summarized using descriptive statistics. “Percent seizure free days” is defined as the number of days without any seizures (partial or generalized) divided by open-label duration in days, in percent. This percentage will be classified into [0, 25), [25, 50), [50, 75), [75, 95), [95, 100), [=100] and described statistically. The most upper class represents completely seizure free patients, the next class almost seizure free patients.

Additionally, the proportion of subjects who become seizure free for 6 and 12 month rolling intervals will also be determined. That is, a subject who becomes seizure free for any 6 month period of time will qualify for the 6 month metric. A subject who becomes seizure free for any 12 month period of time will qualify for both the 6 month and 12 month metric.

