## 10. STUDY PROCEDURES

### 10.1. Study Flow Chart

As presented in the Study Flow Chart (see Appendix A), Study Visit 1 will have a window range of  $\pm 3$  days. After Study Visit 1, all remaining study visits will have a window range of  $\pm 7$  days around that visit day to accommodate individual schedules, as follows:

- Baseline for the open-label extension study corresponds to the assessments performed at the last visit of the Maintenance phase (Visit 9) of Study VRX-RET-E22-302 for all patients. The final, baseline eligibility assessment for the open-label extension study, including obtaining informed consent and dispensing open-label study medication will be performed at the last visit of the Transition phase (Visit 11) of Study VRX-RET-E22-302.
- Study Visit 1 (at Month 1  $\pm 3$  days)
- Study Visit 1a for Hematological Monitoring (at Month 2  $\pm 7$  days)
- Study Visit 2 (at Month 3  $\pm 7$  days)
- Study Visit 2a for Hematological Monitoring (at Month 4  $\pm 7$  days)
- Study Visit 3 (at Month 6  $\pm 7$  days)
- Study Visit 3a for Hematological Monitoring (at Month 8  $\pm 7$  days)
- Study Visit 4 (at Month 9  $\pm 7$  days)
- Study Visit 4a for Hematological Monitoring (at Month 10  $\pm 7$  days)

- Study Visit 5 (at Month 12  $\pm$ 7 days).
- Study Visit 6 (at Month 16  $\pm$ 7 days)
- Study Visit 7 (at Month 20  $\pm$ 7 days).
- Study Visit 8 (at Month 24  $\pm$ 7 days).
- Study Visit 9 (at Month 28  $\pm$ 7 days).
- Study Visit 10 (at Month 32  $\pm$ 7 days).
- Study Visit 11 (at Month 36  $\pm$ 7 days).
- Study Visit 12 (at Month 40  $\pm$ 7 days).
- Study Visit 13 (at Month 44  $\pm$ 7 days).
- Study Visit 14 (at Month 48  $\pm$ 7 days).

Each study month will be defined as 30 calendar days. If a patient visit occurs outside the visit window, the study clinical monitor (CRA) should be notified and the reason for the deviation noted. An attempt should be made to ensure that the patient returns for subsequent visits on schedule using the last visit of the Transition phase (Visit 11) of Study VRX-RET-E22-302, which corresponds to the final, baseline eligibility visit for the open-label extension study.

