**10.15. Study Visits after the First Year**

After the first year of open-label extension study, the study visits will occur every 4 months (3 visits per year), and will continue until retigabine is approved and

commercially available, or until the program is discontinued. The assessments for the first 2 study visits of each year will be identical, and the assessments for the last study visit of each year will be identical. To provide guidance, the following study visits and assessments will be performed during the second and third years of the open-label extension study:

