### **11.4.2. Handling of Missing Data**

No imputation will be made for missing data in the safety analyses, with the exception of incomplete date variables regarding adverse events onset date that is necessary for defining treatment-emergent adverse events. More details on imputation of partial dates will be provided in the statistical analysis plan.

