**CONFIDENTIAL**

RM2009/00475/00  
VRX-RET-E22-304

---

Program Path/sas program name

Run Date:

---

Filename: 87272\_304\_SAP\_v2\_final

page 103 of 148

LISTING 8 GENERALIZED OR UNCLASSIFIED SEIZURE FREQUENCY

PATIENT ID	AGE/GENDER/RACE	VISIT	DID SEIZURES OCCUR SINCE LAST VISIT	DATE OF SEIZURE (STUDY DAY)	ABSENCE SEIZURES	MYOCLONIC SEIZURES	TONIC-		PARITAL STATUS EPILEPTICUS	CONVULSIVE		UNCLASSIFIED SEIZURES
							CLONIC SEIZURES	ATONIC		STATUS EPILEPTICUS	STATUS EPILEPTICUS	

This section contained data from each individual patient, rather than in aggregate. They have been excluded to protect patient privacy. Anonymized data from each patient may be made available subject to an approved research proposal. For further information please see the Patient Level Data section of the Sponsor Clinical Study Register.

105

CONFIDENTIAL

RM2009/00475/00  
VRX-RET-E22-304

Valeant Pharmaceuticals North America  
Protocol Number: VRX-RET-E22-304

PAGE X OF X

106

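### SAP 4.4 divides seizures and seizure-free days by the whole open-label duration, so a visit interval with no diary data counts as seizure-free time

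*SAP*

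**What the plan says.** SAP 4.4 defines the monthly total partial seizure rate as "the sum of total partial seizures throughout the open-label portion (of Study VRX-RET-E22-304), divided by open-label duration in days", standardised to 28 days. The monthly total seizure rate has the same form. Percent change from the 8-week Study 302 baseline, its class table, the responder rate (at least a 50% reduction) and the treatment-duration cohorts rest on the partial-seizure rate.

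Percent seizure-free days "is defined as the number of days without any seizures (partial or generalized) divided by open-label duration in days, in percent". Protocol 11.1 likewise takes each patient's own open-label treatment duration as the denominator. For rolling seizure freedom, "a subject who becomes seizure free for any 6 month period of time will qualify for the 6 month metric", and the 12-month metric works the same way.

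None of these definitions requires diary data for the days counted, and no other section supplies the condition:

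- Protocol 11.4.2 says "No imputation will be made for missing data in the safety analyses", apart from incomplete adverse event onset dates. It is silent on efficacy.
- The imputation rules in SAP 4.5.2 cover adverse event dates, severity and causality.
- SAP 4.3 bases percentages on patients providing data, not on days.
- SAP 4.4 derives the baseline rate only for patients who enter the extension "and have a monthly total partial seizure rate during the open-label extension period". That deals with a patient who has no rate at all, not with one who has a rate and an empty interval.

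Diaries are collected and replaced at the main visits, which are 4 months apart after year 1 (Protocol 10.15). The shells for Listings 7 and 8 in SAP section 12 carry a visit-level item, "DID SEIZURES OCCUR SINCE LAST VISIT", but no derivation uses it.

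**The concern.** The numerator holds only recorded seizures, while the denominator holds every open-label day. The SAP never says that missing means zero, but its formula has that effect for the monthly rates.

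For percent seizure-free days the text leaves two readings. If an unrecorded day is a day without seizures, which is the natural reading, the percentage is too high. If it is not, the day still sits in the denominator and the percentage is too low. Two programmers following the same SAP could report different results. On the natural reading, unrecorded time also counts towards the 6- and 12-month metrics.

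Percent change and responder rate are ratios to the Study 302 baseline, so what matters for them is missingness in the extension relative to baseline. They are inflated if diary time is lost more often over several years than over the 8-week baseline. Seizure-free days and rolling seizure freedom have no baseline term to offset the error.

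**Working it through.** The plan has no figure to reproduce: Protocol 11.3 calls sample size not applicable, and neither document estimates diary missingness. The 40% and 80% values and the missing shares below are illustrative assumptions. Unless stated otherwise, unrecorded days are assumed to resemble recorded ones.

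**1. Interval length.** Protocol 10.1: "Each study month will be defined as 30 calendar days". After year 1 an interval is 4 × 30 = 120 days. With ±7-day windows at both ends it is 106 to 134 days.

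**2. One empty interval, complete baseline.** With open-label duration D days and true reduction r, the rate is multiplied by 1 − 120/D. Then:

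- apparent reduction = 1 − (1 − r)(1 − 120/D)
- true reduction that reads as 50% = 1 − 0.5/(1 − 120/D)

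| Duration | D (days) | 1 − 120/D | True 40% reads as | True reduction that reads as 50% |
|---|---|---|---|---|
| 16 months | 480 | 0.750 | 55.0% | 33.3% |
| 24 months | 720 | 0.833 | 50.0% | 40.0% |
| 36 months | 1080 | 0.889 | 46.7% | 43.8% |

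**3. Missing time in both periods.** Let m be the missing share of extension days (assumed 0–20%) and b the missing share of baseline days (assumed 0–10%), with full-duration denominators in both. Then:

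- apparent reduction = 1 − (1 − r)(1 − m)/(1 − b)
- true reduction that reads as 50% = 1 − 0.5(1 − b)/(1 − m)

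| m | b | True 40% reads as | True reduction that reads as 50% |
|---|---|---|---|
| 10% | 0 | 46.0% | 44.4% |
| 10% | 5% | 43.2% | 47.2% |
| 10% | 10% | 40.0% | 50.0% |
| 20% | 10% | 46.7% | 43.8% |
| 5% | 10% | 36.7% | 52.6% |

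The fourth row shows inflation despite baseline gaps. The third shows cancellation and the last a reversed sign.

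**4. Percent seizure-free days.** Take a true 80% with m = 10%. If unrecorded days count as seizure-free, the result is 0.9 × 80 + 10 = 82%. If they do not, it is 0.9 × 80 = 72%. A patient seizure-free throughout 36 months with one empty interval scores either 100% or (1080 − 120)/1080 = 88.9%. The first falls in the completely seizure-free class, the second in [75, 95).

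**5. Rolling metrics, counting unrecorded days as seizure-free.** SAP 4.4 does not say which month length applies, so both are shown.

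| Window | Days | Recorded seizure-free days needed beside one empty interval | Beside two | Beside three |
|---|---|---|---|---|
| 6 months of 30 days | 180 | 60 | 0 | 0 |
| 6 months of 28 days | 168 | 48 | 0 | 0 |
| 12 months of 30 days | 360 | 240 | 120 | 0 |
| 12 months of 28 days | 336 | 216 | 96 | 0 |

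Two consecutive empty intervals (240 days) meet the 6-month metric, and three (360 days) the 12-month metric, with no recorded day.

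**The case against.** **Open-label duration is not defined, so full duration is an inference.** This has little force. Protocol 11.1 and SAP 4.4 both describe the denominator for seizure-free days as the individual's open-label treatment duration, and nothing limits it to days covered by a diary.

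**For seizure-free days the protocol itself sets that denominator.** This stands in part. Changing the main analysis departs from the protocol wording, so the change must be declared and the original version kept alongside.

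**A trailing gap may already be cut off.** SAP 4.5.1 ends exposure at the last treatment-period visit for a patient lost to follow-up whose drug use is confirmed. That rule governs extent of exposure only. Even if it were carried over, it would not touch a gap in mid-course.

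**Gaps of two or three intervals are unlikely.** Drug and diaries change hands at the same visits, and persistent non-compliance is a ground for withdrawal. This is fair: those cases show what the definition permits, not what to expect. One missing interval needs no such pattern.

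**The visit-level item is imperfect.** It may be answered from recall with the diary lost, and it cannot show days skipped inside an answered interval. This stands, so a completeness figure built on it is an upper bound.

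**The size is assumed, and little depends on it.** This also stands. The missing shares are chosen, the 24-month example falls exactly on the responder cut-off, the handling of Study 302 baseline gaps is not in these documents, and background antiepileptic drugs may change during the extension. These points limit the importance of the problem but do not remove it.

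**Conclusion.** The concern holds. Applied as written, SAP 4.4 treats a visit interval without diary data as time with no seizures in the monthly rates. On the natural reading it does the same for seizure-free days and rolling seizure freedom.

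For one patient the effect can be material: a single empty 120-day interval adds 10 percentage points to a true 40% reduction at 24 months and 6.7 points at 36 months, given a complete baseline and the same seizure rate on unrecorded days. The study-level effect cannot be computed without a missingness rate, and it is zero if diaries are complete. The direction is favourable for the extension rate itself and, on the natural reading, for seizure freedom. For percent change and responder rate it depends on baseline missingness.

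Efficacy is a secondary, descriptive objective, so the reported long-term efficacy figures are affected and no confirmatory test is. The change should be made, but the primary safety objective does not depend on it.

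**What to change.** In SAP 4.4:

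1. Define the denominator of both monthly rates and of percent seizure-free days as open-label days in visit intervals with diary data, meaning the item on seizures since the last visit is answered. Count seizure-free days only within those intervals.
2. Apply the same rule to the Study 302 baseline rate where the data allow, so that both periods use the same kind of denominator.
3. Credit a 6- or 12-month seizure-free interval only if every visit interval in it has diary data, and state the month length.
4. Report diary completeness as the percentage of open-label days in intervals with diary data.
5. Keep the full-duration version as a sensitivity analysis, stating how it treats unrecorded days.
6. Record the change in SAP 4.8, which now reports none.

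The cost is SAP wording, one derived variable from an item already on the listing shells, and one summary table. Days skipped inside an answered interval remain undetected. Results change only as far as whole intervals are missing; if none are, the completeness summary shows it.
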